## 11.4 MEDICAL HISTORY AND MEDICATIONS

	Past Medical History (resolved)	Active diagnosis or problem
Hypertension (high blood pressure)		
Hypertriglyceridemia (high triglycerides)		
Hyperlipidemia (high cholesterol)		
Coronary artery disease (heart disease)		
Polycystic Ovarian Syndrome (PCOS)		
Smoking		
Depression		
Anxiety		
Bipolar disorder		
Stroke		
Transient ischemic attack (TIA or mini stroke)		
Peripheral vascular disease		
Back pain		
Osteoarthritis		
Hypothyroidism		
Asthma		
Chronic Obstructive Pulmonary Disease (COPD)		
Hepatitis B		
Hepatitis C		
Malignancy		
Insomnia or sleep disorder		
List any other past medical history of active diagnosis/problem not listed above.		

List the generic names of each medication you are currently taking.	
---	--

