## 1.2 SCHEMA

## 1.3 SCHEDULE OF ACTIVITIES (SOA)

Study Procedures	En.	Days from Enrollment															
		-14 to 0	0	7	9	30	60	90	120	150	180	210	240	270	300	345	365
Study Window (days)			+ 4	-1 to +5	±14	±14	±14	±14	±14	±14	±14	±14	±14	±14	±14	±14	±14
Baseline Study Visit*		x															
Follow-up Study Visits*											x						x
Consent		x															
Eligibility		x															
Review inclusion/exclusion criteria		x															
PAR-Q Screen (11.1)		x															
Medical Clearance Letter (11.2) if positive PAR-Q screen		x															
Survey Response Collection Method (text, email, in-person)		x															
Reminder phone call, text message, or email prior to visit											x						x
Physical Activity Measurement																	
Actigraph device and instructions provided		x															
ActiGraph wear (consecutive 7-day periods with remote CentrePoint Sync app upload)		x			x	x	x	x	x	x	x	x	x	x	x	x	
Reminder email/phone call/text message (Actigraph instructions)**				x	x	x	x	x	x	x	x	x	x	x	x	x	
Collect Actigraph device and charger from participant																	x
Anthropomorphic Measurements																	
Height		x															
Weight		x									x						x
Laboratory Measurement																	
Screening hemoglobin A1C (point-of-care sample)to -1		x									x						x
Repeat A1C (serum or alternative POC A1C device) if suspected erroneous A1CNow+ reading		x									x						x
Randomization																	
Referral to hDPP		x															
Mail Sweetch digital health kit (research coordinator)			x														

Study Procedures	-14 to 0	0	En.	Days from Enrollment														
				7	9	30	60	90	120	150	180	210	240	270	300	345	365	
Study Window (days)				+4	-1 to +5	±14	±14	±14	±14	±14	±14	±14	±14	±14	±14	±14	±14	
Download/register Sweetch app + sync scale (participant)				x														
Questionnaires/Surveys (text, email, in-person)																		
Demographics (11.3)		x																
Medical history and medications (11.4)		x									x						x	
Exercise stage of change questionnaire (11.5)		x									x							
Self-reported PA information (11.6)**		x			x	x	x	x	x	x	x	x	x	x	x	x		
"Starting the Conversation" Brief Dietary Assessment (11.7)		x									x						x	
Apps and Devices (11.8)		x																
NPART Survey (11.9)		x																

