### 7.2 PARTICIPANT DISCONTINUATION/WITHDRAWAL FROM THE STUDY

The study team will only withdraw a participant if any clinical adverse event (AE), laboratory abnormality, or other medical condition or situation occurs such that continued participation would not be in the best interest of the participant. Participants who develop diabetes mellitus during the course of the study **will be eligible** to continue, and all new medications that are initiated for glycemic control will be reported. Subjects who sign the informed consent form, and are randomized and receive the study intervention, and subsequently withdraw, or are withdrawn or discontinued from the study, will not be replaced.

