#### 9.4.5 COVARIATE ADJUSTMENT

We anticipate that randomization will minimize differences in participant characteristics that may be associated with the primary or secondary endpoints between the two groups. All primary statistical analyses will be unadjusted. However, if we identify differences in participant baseline characteristics, or exposure to potential confounders during the course of the study (e.g. steroid use, antihyperglycemic use), sensitivity analyses will be conducted to include these variables as covariates in multivariable logistic or linear regression models, as appropriate. These adjusted analyses will be viewed as supportive in interpreting the findings of the unadjusted analyses.

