#### 9.4.7 ANALYSIS OF THE PRIMARY EFFICACY ENDPOINT(S)

The primary effectiveness endpoint will be analyzed using an intention to treat approach (ITT) using logistic regression models, where attainment of the CDC's benchmark for type 2 diabetes risk reduction will be the dependent variable and treatment group the

primary exposure variable. Covariate-adjusted models will include any variables that are identified to be statistically significantly different on univariate analysis between the two treatment groups at baseline or over the study period, including use of medications that could influence blood glucose (antihyperglycemics, steroids) and incident diabetes.

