##### **Costs**

Costs will be estimated using a health system perspective and consist of formal healthcare costs and informal healthcare costs in accordance with best practices. Healthcare costs will be estimated using healthcare resources utilized multiplied by prices for resources. We anticipate that healthcare utilization costs during the trial will be similar between arms. Future healthcare utilization costs will be projected based on previously published literature in relation to our metabolic endpoints. We will use patient reported medical history and medication (Section 11.4) and healthcare utilization (Section 11.14) collected baseline, 6 months, and 12 months during the study to quantify healthcare resources utilized. Unit prices will be derived from public database and Medicare fee schedules. We will use published data to supplement cost data including cost estimates for each health state in the Markov model. Intervention costs will be estimated from data provided to us by the company developing the app, Sweetch Health, Ltd. Costs for the human coach intervention in the hDPP arm will be estimated using the Medicare Diabetes Prevention Program (MDPP) billing and fee schedule.

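### Medication form 11.4 records only current use at three visits, so completed courses, single injections and the duration of any drug are mostly not recoverable from it

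*Combined protocol and SAP*

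**What the plan says.** The medication item in Section 11.4 reads "List the generic names of each medication you are currently taking". It asks for nothing else about drugs: no earlier use, start or stop date, dose or reason. The Schedule of Activities (Section 1.3) places the form at baseline, day 180 and day 365.

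Three parts of the plan draw on drug use during follow-up:

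- Section 9.4.5 plans sensitivity analyses if the arms differ in "exposure to potential confounders during the course of the study (e.g. steroid use, antihyperglycemic use").
- Section 9.4.7 puts into the adjusted models for the primary endpoint any variable that differs between arms "at baseline or over the study period, including use of medications that could influence blood glucose (antihyperglycemics, steroids").
- Section 9.4.9 (Costs) multiplies resources used by prices and states "We will use patient reported medical history and medication (Section 11.4"), along with the utilization form, "collected baseline, 6 months, and 12 months during the study to quantify healthcare resources utilized".

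Two further places state an intention to collect drug data. Section 7.2, in its sentence on participants who develop diabetes, says that "all new medications that are initiated for glycemic control will be reported". Section 10.1.11.1 lists concomitant medications among the clinical data entered into REDCap. Neither names a form, dates or timing.

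On the weight of the adjusted results, Section 9.4.5 is explicit: "These adjusted analyses will be viewed as supportive in interpreting the findings of the unadjusted analyses".

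**The concern.** The adjusted analyses need to know who was exposed at any time in the year. The costing needs to know how much was used. A list of drugs in use on the visit day answers neither question for a course that has already ended, and it gives no quantity for a course that continues.

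If the exposure variable is built from this form alone, a participant who took and finished a steroid course between visits counts as unexposed. Section 9.4.7 brings in medication use only where the arms are found to differ, so a real difference in short courses could go unseen and never enter a model. For the costing, a drug name without dose or dates leaves nothing to multiply by a price.

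**Working it through.** The plan states no figure on this point. The check therefore has two parts: whether any other instrument fills the gap, and how large the gap is.

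**1. Other instruments shown**

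- Healthcare utilization (11.14): asks about visits, hospital stays and emergency use over the past 6 months. It has no drug item.
- Adverse event evaluation (11.21): asks about new medical problems since the last visit, not treatments.
- Record review (8.3): covers screening and adverse event assessment.
- Sections 7.2 and 10.1.11.1: state that drug data will be reported or entered, with no form and no schedule row other than 11.4.

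None of the forms shown asks about drugs taken between visits.

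**2. Share of courses still running at a follow-up visit**

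Inputs: visits at days 180 and 365 (Section 1.3). Assumptions of this review: one course of *d* days, with its start equally likely on each of days 1 to 365, listed only if it covers a visit day. For *d* up to 180, *d* start days cover day 180 and another *d* cover day 365, so the share is 2*d*/365.

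| Course length | Calculation | Share listed |
|---|---|---|
| 1 day (e.g. one injection) | 2/365 | 0.5% |
| 7 days | 14/365 | 3.8% |
| 14 days | 28/365 | 7.7% |
| 30 days | 60/365 | 16.4% |
| 60 days | 120/365 | 32.9% |
| 90 days | 180/365 | 49.3% |
| 180 days | 360/365 | 98.6% |

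A drug started in the study and continued to the next visit is listed in every case.

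**3. Courses near the end of the study**

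Use close to the 12-month measurements matters most. Section 6.5 uses a 3-month window for these drugs, taken here as 90 days. For starts within days 276 to 365 the share is *d*/90: 7/90 = 7.8%, 14/90 = 15.6%, 30/90 = 33.3%. Most short courses are still missed.

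**4. Duration of a drug that is listed**

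The start date is unknown. Averaged over start days, the gap from start to next visit is (180 × 89.5 + 185 × 92)/365 = 90.8 days, and at most about 6 months. For uninterrupted use, counted to day 365:

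- First listed at 6 months and again at 12: a start on day 180 gives 186 days of use and a start on day 1 gives 365, a ratio of 365/186, about 2.
- Listed only at 12 months: anywhere from 1 day (start on day 365) to 185 days (start on day 181).

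Dose is unknown in both cases.

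**The case against.** The strongest reply has four parts.

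- **Continuing drugs are seen.** Glucose-lowering drugs begun after a diabetes diagnosis are usually continued, and the form lists them at the next visit. This stands. A reader might infer that most drug exposure goes unrecorded, or that anyone treated between visits is coded unexposed. The documents do not support that; it holds only for courses that ended before the visit.
- **Other routes are promised.** Sections 7.2 and 10.1.11.1 commit to collecting glycemic and concomitant drugs, and the adverse event question may bring to light illnesses that led to a steroid course. This stands in part. It is not shown that the trial cannot identify exposure, only that no instrument for doing so is named. Section 7.2 also does not cover steroids or weight-loss drugs.
- **The main result does not depend on it.** Primary analyses are unadjusted (Sections 9.3 and 9.4.5), and Section 9.4.9 expects similar healthcare use in both arms. This stands. Nothing in the documents shows that short courses would shift the cost-effectiveness ratio or differ between arms.
- **The percentages describe hypothetical courses.** This also stands: the protocol gives no rate or length of drug use. An even spread of starts also weights a course in month 2 like one in month 11. Restricting to the last 90 days raises the shares but leaves most short courses unseen.

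A reader might also say that the costing rests on two snapshots. Section 9.4.9 names three time points, although only the two follow-up visits can show a drug begun in the study.

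**Conclusion.** The point holds in a limited form. Form 11.4 will mostly miss short or completed courses and single injections: under an even spread of start dates it lists about 4% to 16% of courses lasting 7 to 30 days. It cannot give the start, duration or dose of any drug, including those it lists. Courses of 180 days or more are nearly all listed.

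The effect is confined to the supportive adjusted analyses and the in-trial drug quantities. If both arms had 30-day courses with equal capture, a true difference between arms in the share exposed would appear at about one sixth of its size. It would be wrong to infer that the primary comparison is compromised, because drug exposure does not enter that analysis. The number of participants affected cannot be estimated from the documents.

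Separately, the note in Section 6.5 that one joint injection leads to withdrawal and the narrower withdrawal rule in Section 7.2 do not agree and must be reconciled.

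**What to change.** At the 6- and 12-month visits, add an item to Section 11.4 asking whether the participant has taken any glucose-lowering drug, weight-loss drug, or steroid tablet or injection (list in Section 6.5) since the last study visit. Record the drug name, start date and stop date, and the dose for costing. State in Sections 9.4.5 and 9.4.7 that the exposure variables are derived from these dates, and in Section 9.4.9 that the quantities of these drugs are too.

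If a separate concomitant medication form already exists, name it, add it to the Schedule of Activities, and confirm that it records dates and dose and covers the period since the last visit. That would meet the commitments in Sections 7.2 and 10.1.11.1.

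The cost is a minute or two more at each of two existing visits, with no new visit or staff. The answers will carry recall error over about six months, as the utilization form already does.

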## 11.5 EXERCISE STAGE OF CHANGE QUESTIONNAIRE

## Exercise Stage of Change Questionnaire (4-item)

For each of the following questions, please select Yes or No.

Physical activity or exercise includes activities such as walking briskly, jogging, bicycling, swimming, or any other activity in which exertion is at least as intense as these activities.

1. I am currently physically active (at least 30 minutes per week).	 Yes
	 No
2. I intend to become more physically active in the next 6 months.	 Yes
	 No

For activity to be regular, it must add up to a total of 30 minutes per day and be done at least 5 days per week. For example, you could take one 30-minute walk or take three 10-minute walks for a total of 30 minutes.

3. I currently engage in regular physical activity.	 Yes
	 No
4. I have been regularly physically active for the past 6 months.	 Yes
	 No

## Scoring Key:

- No to 1, 2, 3, and 4 = Pre-contemplation stage
- No to 1,3, and 4, Yes to 2= Contemplation stage
- Yes to 1 and 2, No to 3 and 4= Preparation stage
- Yes to 1 and 3, Yes or No to 2, No to 4= Action stage
- Yes to 1,3, and 4, Yes or No to 2= Maintenance stage

## 11.6 SELF-REPORTED PHYSICAL ACTIVITY

Administered via electronic survey or phone call in the week preceding Actigraph measurement.

How many minutes of moderate or brisk physical activity did you complete in the preceding week? Examples of moderate or vigorous activity can be found here .	(Be sure to report your activity in total minutes per week, NOT hours. For example, if you exercised for 30 minutes on 5 days in the past week, enter 150.)
Please provide any comments about your physical activity in the past week (optional).	

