## 3.3 SECONDARY ENDPOINTS

Secondary endpoints will include:

- Primary endpoint assessed using self-reported PA data in lieu of objectively measured PA data (Actigraphy).
  - In this trial, PA will be assessed using both participant self-reported data and Actigraphy. While the CDC relies on participant self-reported PA data for outcome assessment, in this trial, there is a potential bias introduced from using self-reported PA data alone since the dDPP arm will have access to objective PA data while the hDPP group may or may not (depending on their personal use of wearable devices or fitness tracking apps). Studies have shown over-estimation of PA by self-report. Considering that the CDC accepts self-reported PA data, we

will also analyze results of the primary endpoint using self-reported PA data collected at same interval as serial Actigraphy.

- Change in A1C from baseline to 6 months and 12 months
- Absolute and percentage weight change from baseline to 6 and 12 months
- Changes in physical activity measures (average minutes/week of physical activity, MET-hours per week of physical activity, average number of steps per day) at 6 months and 12 months
- Incident type 2 diabetes (A1C  $\geq 6.5\%$ )
- Engagement level
  - The **dDPP engagement score** will be calculated as the percentage of full weeks during which the app was installed and a) both push notifications and motion sensors were enabled OR b) participant accessed any content within the app.
  - The **hDPP engagement score** will be calculated as a percentage of sessions attended. Per CDC definitions of engagement, the number of required hDPP sessions for months 1-6, 7-12, and 1-12 will be 8, 3, and 11, respectively. For participants who attend more than the required number of sessions across each of these intervals, the engagement score will be capped at 100%. A participant who attends 4 out of 8 sessions in months 1-6 and 1 out of 3 sessions in months 7-12 would receive an engagement score of 50% (4 out of 8 sessions in months 1-6), 33% (1 out 3 sessions in months 7-12), and 45% (5 out of 11 sessions in months 1-12).

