### 8.2.3 PHYSICAL ACTIVITY MONITORING

Participants will be provided an ActiGraph (either GT9X-BT link or CPIW) wrist monitor and asked to wear the device for 7-days of consecutive wear time at enrollment and once approximately every 1 month thereafter for the duration of the study. A reminder email, phone call, or text message one day prior to the scheduled event and on the day of event will be sent by our team.

Participants will return the ActiGraph device at the 12-month visit. If the actigraphy wrist monitor or accessories are damaged during a scheduled wear period, replacement device or accessories will be mailed to the participant.

[figure not shown]
The ActiGraph GT9X-BT Link and CPIW are FDA-cleared devices, which have the ability to distinguish non-wear time from physical inactivity. Both devices capture and record high resolution raw acceleration data, which are converted into a variety of objective activity measures. The CPIW, which is the newer model of the ActiGraph wrist monitor, has an extended 30-day battery life allowing

for continuous wear time during the scheduled wear period, which minimizes participant burden and the potential for missing data associated with frequent device charging. ActiGraph provides a cloud based service platform, CenterPoint, which allows automated capture of actigraphy data from the ActiGraph monitor. The participant will be blinded to the Actigraph data.

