At the baseline visit, participants will be provided 1) the ActiGraph activity monitor, 2) Centrepoint (CP) data hub, 3) charging dock, 4) power cable and 5) USB Cable (see screenshot below), and a participant guide will be provided with clear instructions on how to use these devices. The CentrePoint data hub uses 3G cellular network (paid for by study team) to transmit data collected from the ActiGraph activity monitor to the study team via the CentrePoint cloud-based software. The participant's home WiFi will not be utilized for the remote data capture. The CentrePoint datahub uses Bluetooth technology to automatically capture data from the ActiGraph device when the participant is in close proximity to the datahub. Participants will also be asked to upload the raw data collected from the ActiGraph activity monitor to the CenterPoint data hub after each wear period by connecting the physical activity monitor to the data hub using a provided USB cable/charging dock (see screenshot below). This physical connection will provide the raw data required by the study team. The study team will track study participant compliance remotely using the CentrePoint software, which will indicate Bluetooth captured data as well as manual data upload to the data hub.

If the study team does not see that the participant is wearing their physical activity monitor, we will contact the participant by text message, email, or phone call to remind them to wear the device, ensure that the data hub is plugged in, and/or encourage the participant to upload data from their activity monitor to the datahub. If data show that fewer than 75% of the 7-day period comprised actual wear time, participants will be asked to repeat the consecutive 7-day period as soon as this is noted, and the previously collected incomplete/invalid data will be disregarded. Once the participant has been deemed compliant, a message or email will be sent to communicate that they have satisfactorily completed their 7-day wear period.

This screenshot shows the accessories that will be provided to study participants at the baseline visit for physical activity tracking.

This screenshot shows the connection between the activity monitor/charging dock to the CP Data hub, which will occur after every 7-day wear period to upload raw data to the Centerpoint cloud software, which is accessible by the study team.

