#### 8.2.4 SELF-REPORTED PHYSICAL ACTIVITY DATA

For participants who agree to complete surveys electronically, a Redcap electronic survey will be emailed to participants 7 days after each scheduled Actigraph assessments to collect the number of minutes of moderate or brisk physical activity completed during the preceding week. If a participant reports doing no activity during the preceding week, then zero (0) minutes will be recorded. If participants do not respond to the email survey, the research coordinator will contact the participant by phone to collect this information. There is a potential that a participant who has not been compliant with the scheduled wear period will be asked to self-report PA in a week that they were not also wearing the actigraph device, which will limit our ability to correlate self-report to objectively measured PA in all instances; however, we suspect that averaged on the 12 month period of the trial, self-reported PA in a close window of time relative to the actigraph wear period will correlate with objectively measured PA within an approximate window of time.

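### Sections 8.2.4 and 11.6 time the self-reported activity survey on opposite sides of the Actigraph week, so recall and wear may share no days and the validation correlation would be too low

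*Combined protocol and SAP*

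**What the plan says.** Two places set the timing of the same item.

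- Section 8.2.4: the online form "will be emailed to participants 7 days after each scheduled Actigraph assessments to collect the number of minutes of moderate or brisk physical activity" over the preceding week. The coordinator phones those who do not reply.
- Section 11.6, above the item itself: "Administered via electronic survey or phone call in the week preceding Actigraph measurement". The item reads "How many minutes of moderate or brisk physical activity did you complete in the preceding week".

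Section 8.2.3 asks participants to "wear the device for 7-days of consecutive wear time at enrollment and once approximately every 1 month thereafter". If under 75% of the period was actual wear, "participants will be asked to repeat the consecutive 7-day period as soon as this is noted", and the first data are set aside. No repeat survey is described.

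Section 8.2.4 acknowledges one mismatch: someone who missed the scheduled wear may be "asked to self-report PA in a week that they were not also wearing the actigraph device". It accepts that this limits the correlation and expects 12-month averages to correlate anyway.

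Two uses depend on these data. The synopsis and sections 3.1.6 and 3.3 make correlation of self-report with Actigraphy a secondary objective and endpoint. Section 3.3 also says the team "will also analyze results of the primary endpoint using self-reported PA data collected at same interval as serial Actigraphy". Section 9.4.8 names no analysis for the validation: neither the unit (single week or average) nor a rule for pairing weeks.

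**The concern.** Staff cannot follow both sections. If the appendix line is followed, every participant at every period recalls a week before the device was worn. The validation treats Actigraphy as the gold standard, so comparing different weeks adds real week-to-week change in activity to reporting error. The correlation falls for a reason unrelated to how well people report. The trial could then understate the validity of the type of measure that, by section 3.1.6, the CDC accepts from programs. Recall of the wear week that was never requested cannot be recovered later.

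**Working it through.** The plan states no expected correlation, so there is no figure to reproduce. The sample size (138 per arm, 184 after 25% attrition) does not depend on this point.

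**Step 1: overlap in days.** Number the wear days 0 to 6. A survey answered on day s recalls days s-7 to s-1.

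| Reading | Survey day | Days recalled | Overlap |
|---|---|---|---|
| 11.6, week before wear | -7 to -1 | all before day 0 | 0 of 7 |
| 8.2.4, counted from start of wear | 7 | 0 to 6 | 7 of 7 |
| 8.2.4, counted from end of wear week | 14 | 7 to 13 | 0 of 7 |

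Counting from the last wear day itself gives day 13, recall of days 6 to 12, and 1 day of overlap. The item names no dates, so even under the favorable reading an answer given d days late overlaps on 7 - d days. The Schedule of Activities appears to mark both items in the same columns, but the table is damaged in the text available and was not relied on.

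**Step 2: effect on the correlation.** Let ρ be the share of weekly activity variance that lies between persons (week-to-week reliability). Assume exchangeable weeks and reporting error independent of activity. The variances are the same for matched and unmatched weeks; only the covariance changes.

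- Single week: unmatched r / matched r = ρ.
- Average of k periods: ratio = ρ / [ρ + (1 - ρ)/k], with k = 11 for months 1-11.

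The documents give no ρ. An assumed range of 0.5 to 0.8 gives:

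- Single week: ratio 0.50 to 0.80, a loss of 20-50%. For example, a same-week correlation of 0.6 (assumed) becomes 0.6 × 0.5 = 0.30 to 0.6 × 0.8 = 0.48.
- 11-period average: 0.5/(0.5 + 0.5/11) = 0.92 and 0.8/(0.8 + 0.2/11) = 0.98, a loss of about 2-8%.

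**Step 3: simulation.** Assumed inputs: 11 periods, weekly mean 150 min and SD 90, recall error SD 60, over-report of 40 min, ρ from 0.3 to 0.9. Each cell shows matched / non-overlapping weeks.

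| ρ | Single-week r | r of 11-period averages | Mean self-report ≥150 min/week |
|---|---|---|---|
| 0.3 | 0.83 / 0.25 | 0.95 / 0.78 | 75.7% / 75.9% |
| 0.5 | 0.83 / 0.42 | 0.97 / 0.89 | 72.0% / 72.1% |
| 0.7 | 0.83 / 0.58 | 0.97 / 0.94 | 69.6% / 69.5% |
| 0.9 | 0.83 / 0.75 | 0.98 / 0.97 | 67.7% / 67.7% |

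The correlations follow the formulas. The share reaching 150 min/week by self-report does not move.

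**The case against.** The intended timing can be inferred. Section 8.2.4 is the procedural section, and its caveat about non-compliant wearers makes sense only if compliant wearers report on the wear week. On that view 11.6 is one stray line in a questionnaire appendix. The inference is reasonable, but it leaves the start-or-end question open, and the conflicting line sits on the item itself.

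The mismatch after missed or repeated wear is already disclosed in 8.2.4, with reliance on 12-month averaging. That stands: it is a stated limitation, not an oversight. It does not cover compliant participants, whom 11.6 would misalign. Averaging does remove most of the loss, as Step 2 shows, but the plan does not commit to averages as the unit of the validation.

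Sending the survey only once valid wear is confirmed would do harm. Self-report would then be missing wherever Actigraphy is missing, and section 9.4.2 already expects more missing data there. A validation restricted to matched weeks also selects adherent wearers. Both points stand and shape the fix.

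A reader might infer that the self-report version of the primary endpoint is distorted too. The documents do not support this. Section 3.3 asks for the same interval, not paired weeks. Section 3.2 averages activity over months 1-11, and the criterion decides the outcome only for those with at least 4% but under 5% weight loss who do not qualify on A1C.

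**Conclusion.** The timing rule is wrong as written. Sections 8.2.4 and 11.6 contradict each other, and 8.2.4 lacks an anchor for its 7 days. Depending on the reading, recall and wear share all 7 days or none, for compliant participants as well. This conflict rests on the text alone and is certain.

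The consequence is confined to the validation objective. With ρ assumed at 0.5 to 0.8, the correlation falls by about 20-50% if single weeks are the unit and about 2-8% if 11-period averages are. The larger range should not be read as the expected loss in the trial, because 8.2.4 looks to averages over 12 months. Both ranges rest on an assumed ρ, exchangeable weeks and independent reporting error.

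For the self-report version of the primary endpoint, misalignment adds noise but no evident bias, provided timing is the same in both arms. Week matching would matter there only if the two methods' classifications were compared within person.

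**What to change.** 1. Delete the timing line in 11.6.
2. State in 8.2.4 that the survey is sent when the 7-day wear period ends and asks about those dates, named in the question.
3. Keep the scheduled survey for everyone, including participants without valid wear, so that self-report is not lost where Actigraphy is.
4. Re-send the survey after a repeated wear period, asking about the repeated dates. Section 8.2.3 already has the team tracking wear and telling participants when it is complete.
5. Pre-specify a week-matched validation analysis, and report the all-pairs or 12-month-average correlation alongside it, because matched weeks favor adherent wearers.

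The cost is protocol wording, a change to the REDCap survey trigger, and an occasional extra one-item survey. No sample-size figure changes.
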